16.6. Device calibration

During the RESTFUL Study, the stimulation intensity of the investigational device was calibrated separately for each subject and for each leg. The calibration process is designed to identify the maximally effective settings that are comfortable for each subject. For Arm 1 and Arm 3, the same settings from the RESTFUL Study will be used, except in cases where the subject's responses indicate that these intensity levels are too high or too low. In that case, the calibration process may be repeated either in full or in an abbreviated manner. The sponsor may administer the calibration and/or assist in administering the calibration.

Each time new stimulation units are provided to a subject during this study, such as with replacement devices, they must be programmed with the specific calibrated settings corresponding to that subject.

16.7. Baseline Assessments

Since this is an extension study to the RESTFUL Study, many of the baseline assessments for a given subject in Arm 1 and Arm 2 will refer to assessments completed during the RESTFUL Study, including the following: IRLS [12], Subject characterization, Medical history, Refractory characterization, MOSSleep (Medical Outcomes Study Sleep Scale [13]), and Concomitant medications. Subjects who have a delay between their participation of the RESTFUL study and the CT-05 Extension Study (e.g. Arm 3 participants) will have some or all baseline assessment(s) repeated or re-affirmed.

16.8. Device training

Investigational Plan, Protocol CT-05 (Extension Study)

Document #: CT-4

Rev: 1.0

Effective: 11/24/2021

Subjects will have already received training on device usage in The RESTFUL Study. For subjects in Arm 3, due to the delay between The RESTFUL Study and Arm 3, training reminders may be needed on proper usage of the device, including positioning of the devices on their legs. Instrument(s) designed for marking the human skin (body-marking pen or temporary tattoo) may be employed to mark the locations of electrode placement. Device calibration may be adjusted during device training based on subjective feedback from the subject.

16.9. Study Treatment Description

For Arms 1 and 3 (but not Arm 2), study subjects are instructed to self-administer treatment nightly as needed — typically after RLS symptoms start and before RLS symptoms become severe. The instructions for timing of device use may be adjusted based on the timing of RLS symptoms experienced by the subject. Once activated, a single session of treatment may run for approximately 30 minutes and then turn off automatically. Up to 120 total minutes per night may be used. If device battery life limits the number of uses per night, the following two timings of use may be prioritized: (1) at bedtime, to reduce symptoms and thus help with sleep initiation, and (2) when waking up in the middle of the night, to reduce symptoms and thus help with sleep re-initiation. Device intensity is typically set to the calibrated levels, but intensity may be increased if RLS symptoms are especially severe or decreased such as if RLS symptoms are mild.

16.10. Concomitant Medications and Treatments

Concomitant medications and treatments are tracked throughout the study based on subject reported data. For Arms 1 and 3 (but not Arm 2), study subjects are instructed to maintain a stable dose and schedule of all concomitant medications and treatments for RLS and of all concomitant medications and treatments that affect RLS symptoms, including antidepressants, sleep medications, or sedative antihistamines.

16.11. Leg movement data collection

The NTX100 Neuromodulation System may have the capability to collect data on leg movements, such as by using accelerometers and/or gyroscope sensors, while the subject is wearing the devices. These data may be collected during this study and used for subsequent analysis and development.

16.12. Evaluation and study assessment schedule

Investigational Plan, Protocol CT-05 (Extension Study)

Document #: CT-4

Rev: 1.0

Effective: 11/24/2021

The following evaluation calls and/or visits are scheduled, as outlined in Tables 4 and 6 below. A window of +/- 4 days may be utilized on office follow-ups and a window of +/- 2 days for any phone follow-up, as needed. To reduce self-selection bias, is important to incentivize maximal participation of subjects from the RESTFUL Study in this study. One method to incentivize participation is to reduce the requirement for in-person visits, which can be especially challenging for subjects who do not live within a short distance of the clinical site.

Arms 1 and 3:

Evaluation 1: In-person visit for enrollment, including consent, screening, and assessments. For Arm 1, consent & screening will typically occur on the same visit as Eval 11 for the RESTFUL Study. If the subject's schedule does not permit completion of assessments during this office visit, then these assessments may be conducted via phone follow-up at any time within the 3-days following the office visit.

Evaluation 2: (2-wks after Eval. #1) Phone follow-up to assess RLS symptoms, NTX100 use and assess the occurrence of adverse events and/or changes to daily medications.

Evaluation 3: (4-wks after Eval #1) Phone follow-up to assess RLS symptoms, NTX100 use, and assess the occurrence of adverse events and/or changes to daily medications.

Evaluation 4: (8-wks after Eval #1) In-person visit or Phone call* follow-up to assess RLS symptoms, NTX100 use, and assess the occurrence of adverse events and/or changes to daily medications. Device replacement* and device log analysis may occur at this Evaluation, but this is not a strict requirement.

Evaluation 5: (12-wks after Eval #1) Phone follow-up to assess RLS symptoms, NTX100 use, and assess the occurrence of adverse events and/or changes to daily medications.

Evaluation 6: (16-wks after Eval #1) In-person visit or Phone call* follow-up to assess RLS symptoms, NTX100 use, and assess the occurrence of adverse events and/or changes to daily medications. Device replacement* and device log analysis may occur at this Evaluation, but this is not a strict requirement.

Investigational Plan, Protocol CT-05 (Extension Study)

Document #: CT-4

Rev: 1.0

Effective: 11/24/2021

Evaluation 7: (20-wks after Eval #1) Phone follow-up to assess RLS symptoms, NTX100 use, and assess the occurrence of adverse events and/or changes to daily medications.

Evaluation 8: (24-wks after Eval #1) In-person follow-up to assess RLS symptoms, NTX100 use, and assess the occurrence of adverse events and/or changes to daily medications. Devices are returned at this time.

Evaluation 9: (32-wks after Eval #1) Phone follow-up to assess RLS symptoms, adverse events, and any changes to daily medications. Study exit occurs at this time.

* See Section 16.13 below for discussion of device replacement and in-person visits.

In addition to these assessments, subjects will complete a Weekly Questionnaire each week throughout the 24-wk duration of device usage and a Bi-weekly Questionnaire every 2-weeks from Weeks 25-32.

The schedule of assessments are shown in Table 4 below. Additionally, the devices may automatically log quantitative compliance, usage data, and leg movement data throughout the duration of the study.

Table 4. Schedule of Assessments for Arms 1 and 3

Investigational Plan, Protocol CT-05 (Extension Study)

Document #: CT-4

Rev: 1.0

Effective: 11/24/2021

		Eval 1 Day 0	Wks 1-24	Wks 25-32	Eval 2 Wk-2	Eval 3 Wk-4	Eval 4 Wk-8 In-person or	Eval 5 Wk-12	Eval 6 Wk-16 In-person or	Eval 7 Wk-20	Eval 8 Wk-24	Eval 9 Wk-32
		In-person	Remote	Remote	Remote	Remote	Remote**	Remote	Remote**	Remote	In-person	Remote
Assessment	Completed by											
Screening		X										
Consent		X										
Study entry												
questionnaire	Staff + subject	X										
Weekly questionnaire	Subject		X									
Biweekly questionnaire	Subject			X								
Review weekly												
questionnaire												
responses	Staff				X	Х	X	Х	X	Х	X	
ConMeds	Staff	X			X	X	X	Х	X	Х	X	X
AE Monitoring/Reporting	Staff				Х	Х	X	X	X	X	X	X
RLS	Staff + subject	X (Arm 3 only*)			X	X	X	X	X	Х	X	X
PGI-I	Staff + subject				X	Х	X	X	X	Х	X	X
CGI-I	Investigator + subje	ect					X		X		Х	X
MOS-Sleep	Staff + subject	X (Arm 3 only*)				X	X	Х	Х	Х	Х	X
SF-36	Staff + subject	X									Х	
Device completion												
questionnaire	Staff + subject										X	
Study exit questionnaire	Staff + subject											X
Device replacement Sta	Staff + subject	X **					X **		X **			
		* For Arm 1, data	from Eval	11 of the RE	STFUL Stu	dv will be	used, since bo	th Evals	typically occ	ur on the	same day	

Arm 2:

Evaluation 1: In-person visit or Phone call for enrollment, including consent, screening, and assessments. For Cohort 2A (see Section 16.2), consent & screening will typically occur in-person on the same visit as Eval 11 for the RESTFUL Study. If the subject's schedule does not permit completion of assessments during this office visit, then these assessments may be conducted via phone follow-up at any time within the 3-days following the office visit.

Evaluation 2: (8-wks after completion of the RESTFUL Study) Phone follow-up to assess RLS symptoms, any changes to daily medications, and adverse events.

Evaluation 3: (16-wks after completion of the RESTFUL Study) Phone follow-up to assess RLS symptoms, any changes to daily medications, and adverse events.

Evaluation 4: (24-wks after Eval #1) Phone follow-up to assess RLS symptoms, any changes to daily medications, and adverse events. Study exit.

Investigational Plan, Protocol CT-05 (Extension Study)

Document #: CT-4

Rev: 1.0

Effective: 11/24/2021

As summarized in Table 5, enrollment to Arm 2 will either occur at either 0-wks (EVAL 1), 8-wks (EVAL 2), 16-wks (EVAL 3), or 24-wks (EVAL 4) after completion of the Restful Study, +/- 6-days. If enrollment occurs at 24-wks, the SF-36 and concomitant medication assessments will only be conducted once.

Table 5. Structure of Arm 2

Delay after RESTFUL study completion	Evals conducted
0-wks	1,2,3,4
8-wks	1,2,3,4
16-wks	1,3,4
24-wks	1,4

TABLE 2: SCHEDULE OF ASSESSMENTS FOR ARM 2

Schedule of assessment	s - Arm 2						
		Eval 1	Eval 2	Eval 3	Eval 4		
		Day 0	Wk-8*	Wk-16*	Wk-24*		
		In-person or					
Assessment	Completed by	Remote	Remote	Remote	Remote		
Screening		Х					
Consent		Х					
Study entry question naire	Staff + subject	X					
ConMeds	Staff	X	х	Х	Х		
AE Monitoring/Reporting	Staff		х	х	х		
IRLS	Staff + subject		х	х	х		
PGFI	Staff + subject		Х	Х	Х		
CGFI	Investigator		х	Х	Х		
MOS-Sleep	Staff + subject		Х	Х	Х		
SF-36	Staff + subject	X			Х		
Study exit questionnaire	Staff + subject				х		
* Duration after Eval 11 of The	RESTF UL Study, not CT-4 enrollm	ent [not all subjects will en	roll in time	to complet	e Wk-8 or \	Wk-16 timepoints	

16.13. Device replacement in Arms 1 and 3

The investigational device may include components that are consumable or semi-consumable and may be replaced on a periodic or as-needed basis. Such device component replacement may occur via an in-person exchange or via delivery to the subject. At entry to Arm 1, subjects may continue using investigational device components from the RESTFUL Study prior to replacement – which may require one additional visit for in-person exchange or may be conducted via delivery to the subject.

Investigational Plan, Protocol CT-05 (Extension Study)

Document #: CT-4

Rev: 1.0

Effective: 11/24/2021

Typically, at Evals 4 and 6, stimulation unit replacement will occur and device log data will be downloaded to assess quantitative compliance and usage data and follow-up with the subject regarding usage data. To facilitate this process, subjects will be encouraged to attend an in-person visit. For subjects who live further from the site and/or cannot easily travel to the site, replacement device components will be delivered to the subject and the subject will return used stimulation units to the site for device log data analysis. For these subjects, the Eval may be split into two parts, where the second part is conducted upon receipt of stimulation units at the site and involves a call to follow-up with the subject regarding usage data.

Each time new stimulation units are provided to a subject during this study, they must be programmed with the specific calibrated settings corresponding to that subject.

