5.0 STATISTICAL CONSIDERATIONS

5.1 General Methodology

The statistical analysis of the data obtained from this study will be performed using R statistical software version 4.2.1 or higher. Descriptive statistics may be calculated using Microsoft Excel instead of R.

Data collected in this study will be documented using summary tables and subject data listings. For all efficacy analysis, continuous variables will be summarized using descriptive statistics, specifically the mean, median, standard deviation, minimum and maximum. Categorical variables will be summarized using frequencies and percentages. For continuous data, the minimum and the maximum will use the same decimal place accuracy as the raw data. The mean, median, and standard deviation will be reported to a minimum of one more decimal place than the raw data; statistics for sub-scores may be reported to two more decimal places than the raw data. For categorical data, percentages will be reported to one decimal place. P-values will be reported to 4 decimal places. P-values less than 0.0001 will be displayed as <0.0001 in the tables. All statistical tests for efficacy will be performed at the one-sided 0.025 significance level, and all statistical tests for safety (adverse events) will be performed at the two-sided 0.05 significance level.

For all tables comparing efficacy outcome measures between Arm 1 and Arm 2, effect sizes will be summarized based on Cohen's d for means and Cohen's h for proportions. Additionally, for all tables comparing efficacy outcome measures between Arm 1 Week 24 and CT-05 study entry, effect sizes will be summarized based on Cohen's d for means and Cohen's h for proportions.

Data listings will be sorted by Arm, site number, and subject ID number.

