8.3 Safety Analyses

The proportion of subjects having one or more adverse events (AEs) between study entry and Week 24 will be presented by Arm. The proportion of subjects reporting AEs between Week 25 and Week 32 will be presented for Arm 1. Similar analyses will be done for serious adverse events (SAEs), device-related SAEs, and device-related AEs

Adverse events will be coded using the Medical Dictionary for Regulatory Activities (MedDRA). AEs will be summarized at the subject level using counts and percentages by MedDRA system organ class (SOC) and preferred term (PT). AEs will also be summarized at the event level using

counts and percentages by SOC/PT and seriousness, by SOC/PT and severity, and by SOC/PT and relationship to the device.

Frequency charts of adverse events occurring at any time during the study will be produced. The proportion of subjects with at least one AE will be presented overall and by SOC. The proportion of subjects with at least one occurrence of individual AEs will be presented for AEs occurring in >3% of subjects overall or within either Arm.

This document, when printed, is valid only until its new revision gets released, or when it becomes obsolete in the eQMS. The user of a printed copy of this document is responsible for using the current revision and for discarding superseded or obsolete revisions. The most current version of this document always resides in the eQMS.

Noctrix Health, Inc. CONFIDENTIAL CL-7 v2.0

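### At equal true risk, the any-AE proportions that SAP 8.3 presents by arm are expected to be lower in Arm 2, which is asked less often and followed for less time

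*Protocol*

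**What the plan says.** In Arm 1, AE inquiry begins at the second evaluation, whose entry reads "2-wks after Eval. #1) Phone follow-up to assess RLS symptoms, NTX100 use and assess the occurrence of adverse events and/or changes to daily medications". It recurs at Evaluations 3 to 7 and ends, for the device period, at the in-person Evaluation 8: "assess the occurrence of adverse events and/or changes to daily medications. Devices are returned at this time". Table 4 of the protocol shows the same pattern: Weeks 2, 4, 8, 12, 16, 20 and 24. Arm 1 also has more contact of another kind: "subjects will complete a Weekly Questionnaire each week throughout the 24-wk duration of device usage".

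In Arm 2, the AE row of the schedule is marked only at Evaluations 2, 3 and 4 (Weeks 8, 16 and 24), all remote. The Evaluation 2 entry reads "8-wks after completion of the RESTFUL Study) Phone follow-up to assess RLS symptoms, any changes to daily medications, and adverse events". Entry to Arm 2 is staggered: "enrollment to Arm 2 will either occur at either 0-wks (EVAL 1), 8-wks (EVAL 2), 16-wks (EVAL 3), or 24-wks (EVAL 4". Table 5 then drops the contacts that have already passed.

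Protocol section 10 has AEs recorded from enrolment to study exit, either volunteered by the subject or found by site staff, with onset and end dates.

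On analysis, SAP 8.3 states: "The proportion of subjects having one or more adverse events (AEs) between study entry and Week 24 will be presented by Arm". The SAP's Safety Analysis Population is everyone enrolled, and SAP 5.2 rules out covariate adjustment. SAP 5.1 adds that "all statistical tests for safety (adverse events) will be performed at the two-sided 0.05 significance level". Neither document gives an exposure adjustment, a matched-contact analysis or a caveat about unequal ascertainment.

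**The concern.** The proportion of subjects with at least one recorded AE depends on three things: how often events occur, how long each subject is under collection, and how often someone asks. The second and third differ between the arms by design, and the SAP statistic corrects for neither.

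Arm 2 is the only no-device background rate for this period. If it is under-recorded, a reader of the by-arm table would see an excess in Arm 1 that comes partly from the contact schedule and the late entry of Arm 2 subjects. Mild, short events are the most exposed to this, and protocol section 9.1 describes the anticipated device observations as usually mild to moderate and transient. The by-arm layout is the SAP's own addition: protocol section 17.3.2 pools Arms 1 and 3 and bases safety on treated subjects.

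**Working it through.** Neither document states an AE rate, a recall rate or a sample size, so there is no planned figure to reproduce. The counts below come from the documents; the recall model is an assumption.

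**1. Inquiries by Week 24** (protocol Table 4, Table 5 and the Arm 2 schedule)

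| Group | AE inquiries | Weeks under AE collection to Week 24 |
|---|---|---|
| Arm 1 | 7 | 24 |
| Arm 2, enrolled at 0 weeks | 3 | 24 |
| Arm 2, enrolled at 8 weeks | 3 (the first falls at enrolment) | 16 |
| Arm 2, enrolled at 16 weeks | 2 (the first falls at enrolment) | 8 |
| Arm 2, enrolled at 24 weeks | 1 (falls at enrolment) | about 0 |

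The mean gap between inquiries is 24/7 = 3.4 weeks in Arm 1 and 24/3 = 8 weeks in Arm 2. Week 24 is counted from RESTFUL completion, as in section 16.2 and the footnote to the Arm 2 schedule. The Arm 2 list in section 16.12 dates Evaluation 4 from Evaluation 1 instead. Those places need reconciling.

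**2. Effect of shorter follow-up alone (perfect recall).** Take the same constant event rate in both arms and an assumed true 24-week risk of 40%. With w weeks of collection, the recorded proportion is 1 − 0.6^(w/24).

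- w = 24: 40%
- w = 16: 1 − 0.6^(2/3) = 28.9%
- w = 8: 1 − 0.6^(1/3) = 15.7%
- w = 0: about 0%

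**3. Effect of less frequent questioning alone (Arm 2 enrolled at 0 weeks).** Assume each event is reported at the next scheduled contact with probability 2^(−lag/h), where h is the recall half-life. Over a gap of g weeks, the effective detected time is (h/ln 2)(1 − 2^(−g/h)).

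For h = 4, h/ln 2 = 5.771.

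- Arm 1, gaps 2, 2, 4, 4, 4, 4, 4: 5.771 × (2 × 0.2929 + 5 × 0.5) = 17.81 weeks
- Arm 2, gaps 8, 8, 8: 5.771 × (3 × 0.75) = 12.98 weeks

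At 40% true risk the weekly rate is −ln(0.6)/24 = 0.02128.

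- Arm 1: 1 − exp(−0.02128 × 17.81) = 31.5%
- Arm 2: 1 − exp(−0.02128 × 12.98) = 24.1%

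Other half-lives at 40% true risk:

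| Half-life (weeks) | Arm 1 | Arm 2 (enrolled at 0 weeks) |
|---|---|---|
| 2 | 25.3% | 15.9% |
| 4 | 31.5% | 24.1% |
| 8 | 35.5% | 30.8% |
| 16 | 37.6% | 35.1% |
| Perfect recall | 40% | 40% |

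Across assumed true risks of 20% to 60% and half-lives of 2 to 16 weeks, the artefact is 1.4 to 14.1 percentage points (ratio 1.06 to 1.64).

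**4. Both effects together.** At 40% risk and a 4-week half-life, Arm 2 would read 16.8% for enrolment at 8 weeks and 8.8% at 16 weeks, against 31.5% in Arm 1.

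**The case against.** The case for leaving the plan alone has real weight. Protocol section 17.3.1 makes the safety endpoint descriptive. Each AE is graded for relatedness (section 10.2), and SAP 8.3 reports device-related AEs, SAEs and device-related SAEs separately. Arm 1 is the more closely questioned arm, so the bias makes the device look worse and cannot hide a device risk. The size of the recall effect is assumed, and the model ignores events volunteered between contacts, which section 10 allows. All of this stands and limits the consequence.

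Two stronger readings are tempting, and the documents support neither.

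- A reader might infer from SAP 5.1 that a between-arm AE test is planned and that a significant result would be taken as device harm. SAP 5.1 only sets the level for any safety test; SAP 8.3 names no hypothesis or contrast, and the Arm 1 versus Arm 2 comparison in protocol section 17.2.4 does not list AEs. If such a test were run anyway, with an assumed 25 to 100 subjects per arm, true risks of 20% to 60% and a 4-week half-life, questioning frequency alone would make it significant about 6% to 31% of the time.
- A reader might count the Weekly Questionnaire as a further AE inquiry in Arm 1. Its described uses are symptom nights and device use, and nothing shows that it asks about AEs. It is not counted above.

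What the objection does not remove is the display itself: two crude proportions set side by side, with unequal contacts and unequal follow-up, and nothing to warn the reader.

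**Conclusion.** The point holds in a limited form. The inquiry counts are exact: seven in Arm 1 against three, two or one in Arm 2. Given equal true risk, the recorded any-AE proportion is expected to be lower in Arm 2.

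The shorter follow-up of late Arm 2 enrollees is the more certain cause, because it needs no recall assumption. It does depend on how many enrol late, which the documents do not give, and on Week 24 being counted from RESTFUL completion. The questioning effect disappears only if every event is fully recalled over 8 weeks or is always volunteered. Its size is therefore unknown; the 1.4 to 14.1 points above are a range under stated assumptions and not an estimate.

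SAEs should be little affected by recall, although late entry still shortens the time in which they are collected. The matter concerns how the safety table is presented and read. It does not touch the efficacy analyses or the Arm 1 safety result taken by itself.

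**What to change.** In SAP 8.3:

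- State that all-AE proportions will be neither tested nor interpreted as a between-arm contrast.
- Report, by arm, the number of scheduled AE contacts and the person-weeks of AE follow-up.
- Add a by-arm row for subjects with an AE ongoing on the date of the Week 8, 16 and 24 contacts. Limit each contact's denominator to subjects enrolled and under follow-up before that contact; without this limit, late Arm 2 enrollees stay in the denominator unobserved.
- Give SAEs by arm per person-time.
- Keep the full Arm 1 proportion as the device-arm safety result.

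The cost is SAP wording and one or two table rows. Onset and end dates are already collected, so no new data or visits are needed. The common-contact row omits short events, so it supplements the full table and does not replace it. It also leaves a difference in contact mode, since Arm 1's Week 24 visit is in person and Arm 2's contacts are remote.
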